## 2 BACKGROUND

Langerhans cell histiocytosis (LCH) is a rare disease that may affect any age group. It is regarded as a clonal accumulation and proliferation of abnormal bone marrow derived Langerhans cells. These dendritic cells along with lymphocytes, eosinophils and normal histiocytes form infiltrates typical for the disease which may be found in various organs and at different extent. LCH includes a wide range of clinical presentations comprising the clinical pictures of eosinophilic granuloma, Hand-Schüller-Christian syndrome or Letterer-Siwe disease. The course of disease is unpredictable, varying from spontaneous regression and resolution to rapid progression and death or repeated recurrence and recrudescence with the risk of permanent consequences, defined as irreversible long-term disabilities which are directly linked, predictable and permanent results of the disease upon the patient.

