## **2.3.2 “SPECIAL SITES”**

### **2.3.2.1 “CNS-RISK” lesions**

A retrospective analysis based on 1524 patients registered in the DAL HX-83/90, the LCH I and LCH II studies revealed that involvement of the facial bones or anterior or middle cranial fossa (temporal, sphenoidal, ethmoidal, cygomatic bone, orbital bones) with intracranial tumour extension carry an about 3-fold risk for the development of diabetes insipidus (DI) which is the hallmark of central nervous system involvement in LCH and therefore are called “CNS-RISK” lesions. This was not true for vault lesions.

Based on these data it was concluded that patients with “CNS-RISK” lesions as the only site of disease activity should not be regarded as simple single system disease, because there is usually bone disease with soft tissue tumor and sometimes infiltration of the meninges. Local therapy is usually problematic in such location and these patients should rather receive systemic treatment. The LCH III study protocol offers therapy with

PDN and VBL to these patients.

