## 16.1 DESIGN

### 16.1.1 Group 1 “RISK” patients

The Group 1-Study of LCH-III is a randomized controlled clinical trial for patients with multi-system LCH WITH involvement of “RISK” organs (hematopoetic system, liver, spleen or lungs). The random assignment to the treatment arms will be done in blocks, stratified according to local subcenters to ensure a balance within the local subcenters and within each pre-specified number of treatment assignments (=block). The randomization will be done in the local subcenter without delay after diagnosis.

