### 16.1.2 Group 2 “LOW RISK” patients:

The Group 2-Study of LCH-III is a randomized controlled clinical trial for patients with multi-system LCH WITHOUT involvement of “RISK” organs (hematopoetic system, liver, spleen or lungs) and initial response at week 6 (NAD/AD better).

The random assignment to the treatment arms will be done in blocks stratified according to age at diagnosis ( $\leq 2$  years,  $> 2$  years) and local subcenters to ensure a balance within age groups, the local subcenters and within each pre-specified number of treatment assignments (=block). The randomization will be done in the local subcenter without delay after the first response evaluation 6 weeks after therapy start. Only patients with therapy response, i.e. regression (AD better) or resolution (NAD) after 6 weeks of initial treatment, will be eligible for randomization.

In addition, the impact of a prolonged initial treatment (= course2) for those patients who are not eligible for randomization is examined and compared with the historical control group of LCH-II patients.

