## **16.3 ANALYSES**

The analyses of the primary and secondary endpoints will be done according to the intention-to-treat principle, i.e. the patients will be analyzed in their allocated treatment group, even in case of non-compliance or protocol violations.

The statistical analyses of the primary endpoint will be done with a two-sided significance level of 5 %. The statistical analyses of the secondary endpoints are exploratory. A separate analyses will be performed for each group (“RISK” and “LOW RISK”). In addition to the intention-to-treat analyses a secondary per protocol analyses will be done including all patients who were treated according to the originally assigned treatment arm without protocol violations (= unjustified dose modification, therapy delay and/or improper switch to another therapy within the first 12 months).

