### **16.3.2 Analysis of secondary endpoints**

The overall survival time will be calculated from the date of randomization to death or the last response evaluation.

The reactivation free survival will be calculated from the date of initial response evaluation at week 12. Reactivation (=progression overall and in risk organs after response at week 12) and death will be considered as events. For censored patients the interval will be calculated until the date of the last response evaluation.

The time to non active disease (NAD) will be calculated from randomization to the date of NAD. For censored observation the interval will be calculated until the date of the last follow up information.

The reactivation free survival after NAD will be calculated from the date of NAD. Reactivation (reappearance or progression in any organ) and death will be considered as events. For censored patients the interval will be calculated until the date of last response evaluation.

The time to permanent consequences will be calculated from the date of randomization to the diagnoses of permanent consequences. Deaths without permanent consequences will be censored at the time of death. For all other censored patients the interval will be calculated until the date of the last response evaluation. For the comparison of treatment arms patients with permanent consequences which are already

present at therapy start will not be considered in the analyses.

The proportion of survival, reactivation free survival after response in week 12, reactivation after NAD, the time to NAD and the incidence of permanent consequences will be estimated by the method of Kaplan Meier. The comparison of the randomized arms will be done by log rank-tests.

The proportion of patients with severe organ toxicity (WHO score grade III-IV) within the first 12 weeks of treatment will be compared with Fisher's exact test.

To study the effect of prolonged initial therapy in Low Risk patients without response at week 6. the response rate at week 12 (compared to the status of disease at week 6) will be compared to the response rate at week 12 of the corresponding LCH-II patients. This will be done with Fisher's exact test.

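### The arm comparison of permanent consequences leaves out later, different consequences in patients already affected at therapy start, and in Group 2 prior status is judged about six weeks before time zero

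*Protocol*

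**What the plan says.** Permanent consequences are defined once, in Protocol section 2, as "irreversible long-term disabilities which are directly linked, predictable and permanent results of the disease upon the patient". The definition is generic and no section lists types. The only consequence given a rate is diabetes insipidus (14% in LCH II, time horizon not stated).

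Section 16.3.2 sets the analysis:

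- Time origin: "The time to permanent consequences will be calculated from the date of randomization to the diagnoses of permanent consequences".
- Exclusion: "For the comparison of treatment arms patients with permanent consequences which are already" [...] "present at therapy start will not be considered in the analyses".
- Method: Kaplan-Meier estimates, with log-rank tests between the randomised arms.

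The date of randomisation differs between the two trials. For Group 1 (section 16.1.1): "The randomization will be done in the local subcenter without delay after diagnosis". For Group 2 (section 16.1.2): "The randomization will be done in the local subcenter without delay after the first response evaluation 6 weeks after therapy start".

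Section 6 lists the incidence of permanent consequences in the treatment groups among the overall aims, and sections 6.1.2 and 6.2.1 make their reduction a goal of both randomised trials. Section 16.4 (text below Figure 6) names them among the long-term outcomes to be weighed when the inner boundary has been crossed. Section 16.3 classes all secondary endpoints as exploratory.

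**The concern.** The exclusion treats permanent consequences as one undifferentiated state. A child with diabetes insipidus at therapy start is out of the arm comparison altogether, even if a quite different permanent disability develops later. That later disability is morbidity the trial sets out to reduce. Nothing in the protocol brings it back into the comparison.

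The second problem is timing. A time-to-event analysis needs the at-risk set and the clock to start together. In Group 2 the at-risk set is fixed at therapy start and the clock starts at randomisation, about six weeks later. A first consequence diagnosed in between does not trigger the exclusion, yet its event time is negative. It also cannot be due to the assigned treatment duration, because that had not yet been assigned.

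At stake is whether the comparison answers the question in section 6 for all randomised patients, and whether a few Group 2 events are handled by rule or ad hoc.

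**Working it through.** The protocol states no event count, power or sample size for this endpoint, so there is no planned figure to reproduce. The check is a reading of the rules side by side, followed by illustrations on assumed values.

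**1. Who is removed.** The subject of the exclusion sentence in 16.3.2 is patients. The event is not defined by type, and no rule covers a second, different consequence. The sentence is limited to the comparison of arms; the overall Kaplan-Meier estimate is not expressly restricted.

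**2. When prior status is judged.**

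| | Exclusion judged at | Time zero | Gap |
|---|---|---|---|
| Group 1 | therapy start | randomisation, promptly after diagnosis | none by design |
| Group 2 | therapy start | randomisation after the week-6 evaluation | about 6 weeks |

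**3. Possible number of patients and events left out.** Prevalence at therapy start is not in the documents; 5% to 30% is assumed. Planned maximum sizes are 228 (section 16.5.1) and 148 (section 16.5.2).

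- Excluded, Group 1: 228 × 0.05 = 11.4 to 228 × 0.30 = 68.4.
- Excluded, Group 2: 148 × 0.05 = 7.4 to 148 × 0.30 = 44.4.
- If 10% to 30% of these developed a further consequence (also assumed), the comparison would miss 11.4 × 0.1 = 1.1 to 68.4 × 0.3 = 20.5 in Group 1, and 7.4 × 0.1 = 0.7 to 44.4 × 0.3 = 13.3 in Group 2.

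As a share of all new consequences, with f the prevalence and k the hazard in affected relative to unaffected patients: share = f·k / (f·k + 1 − f). For f = 10%, 20%, 30% this is 10%, 20%, 30% at k = 1, and 18%, 33%, 46% at k = 2. Ranges this wide show that the documents do not settle the size.

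**4. Effect on power.** Assume 40 new consequences in all and a hazard ratio of 0.5 in unaffected patients. Log-rank power = Φ(√D/2 × |ln HR| − 1.96). With all 40 events and HR 0.5 throughout: Φ(3.162 × 0.693 − 1.96) = 59%.

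| Share of events in affected patients | Protocol rule (events excluded) | All patients, HR 0.5 in affected | All patients, HR 1 in affected |
|---|---|---|---|
| 20% | D = 32: 50% | 59% | pooled log-HR 0.8 × 0.693 = 0.555: 42% |
| 33% | D ≈ 26.7: 43% | 59% | pooled log-HR 0.667 × 0.693 = 0.462: 31% |

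If treatment works equally in affected patients, including them raises power. If it does nothing for them, including them lowers it.

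**5. Size of the Group 2 gap.** Take the 14% diabetes insipidus risk from section 2, spread at constant hazard over an assumed T years: λ = −ln(0.86)/T, and P(event in 6 weeks) = 1 − exp(−λ × 6/52).

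- T = 5: 0.35%, or 0.5 of 148.
- T = 2: 0.87%, or 1.3 of 148.
- T = 1: 1.73%, or 2.6 of 148.

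The 148 are patients entering the primary analysis. The number randomised is somewhat larger, which does not change the order of magnitude.

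**The case against.** Restricting an incidence analysis to patients free of the event at baseline is a common and defensible choice. Four stronger readings are tempting, and the documents support none of them.

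- **A breach of intention-to-treat.** Section 16.3 says "The analyses of the primary and secondary endpoints will be done according to the intention-to-treat principle" and explains this as analysis in the allocated group despite non-compliance or protocol violations. The exclusion moves nobody between arms and depends on nothing that happens after randomisation. It neither breaches that principle as stated nor biases the arms.
- **New consequences in affected patients are never counted.** This holds only for the arm comparison. Nothing prevents their collection or description.
- **The rule costs power.** Step 4 of the working shows that the direction depends on the treatment effect in affected patients, which the documents do not give.
- **The trial monitors most closely the very patients it then drops.** The follow-up table in section 13 does not show this. A patient who develops diabetes insipidus after therapy start gets the same brain MRI schedule and stays in the analysis. The 3-monthly schedule reads most naturally as meant for patients with mass lesions, who need have no prior consequence.

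It can also be said that a clock starting at randomisation already implies that earlier events are not incident, and that such date handling belongs in an analysis plan. That is fair as to size. But the protocol fixes the reference date for prior status itself, and in Group 2 it fixes one that does not match the clock.

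What remains is that the exclusion removes whole patients, with no route back for a different consequence, and that the Group 2 dates are misaligned.

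**Conclusion.** The point holds as a minor one on an exploratory secondary endpoint. As worded, the arm comparison omits later consequences of a different type in patients already affected at therapy start. The result then applies only to patients unaffected at that date, which is narrower than the aim in section 6. How many events are lost cannot be derived from the documents; the figures in steps 3 and 4 rest on assumed prevalence, hazards, event count and hazard ratio. The gain from changing the rule is completeness and agreement with the stated aim, not a demonstrated gain in power.

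The Group 2 misalignment follows directly from the text. On the assumptions in step 5 it affects about 0.5 to 2.6 patients, so it is a matter of correct definition and not of material distortion. No sample size, significance level or clinical rule is affected.

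**What to change.** In section 16.3.2, for both groups:

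- Include all randomised patients in the arm comparison.
- Define prior consequences as those diagnosed on or before the date of randomisation, so that the at-risk set and the clock start together.
- Define the event as the first permanent consequence of a type not already present at randomisation.
- Stratify the log-rank test by presence of any permanent consequence at randomisation.
- Keep the comparison in patients free of any consequence at randomisation as a sensitivity analysis.

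Because prior status rests on the date of diagnosis, no extra tests at week 6 are needed. This matters because the response evaluation list in section 10.3 contains no urine osmolality or endocrine test.

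The cost is a change of wording, a short list of consequence types, and coding of each consequence by type. One downside remains: the event pools first and additional consequences, which may dilute the treatment effect if later damage in affected patients is less responsive. The stratification and the sensitivity analysis make this visible but do not remove it.

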### **6.2.3 To assess acute and late treatment toxicity**

## **6.3 GROUP 3: SINGLE SYSTEM MULTIFOCAL BONE AND LOCALIZED “SPECIAL SITES”**

### **6.3.1 To reduce morbidity**

i.e. the rate of reactivation and permanent consequences (as compared to the historical control group of the DAL HX 83/90 and LCH I and II studies).

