### **9.1.2.3 Continuation treatment**

Continuous oral 6-mercaptopurine (6-MP) 50mg/m^2 until the end of month 12 from therapy start.

Pulses of oral prednisone PDN 40mg/m^2 in 3 doses, day 1-5 q 3 weeks, starting at day 1 of week 7 in patients NAD after course 1 or at day 1 of week 13 in patients NAD or

AD better after course 2 until the end of month 12.

Methotrexate 20mg/m^2 orally, once weekly until the end of month 12.

Vinblastine (VBL) 6mg/m^2 i.v. bolus, day 1 q 3 weeks, starting at day 1 of week 7 in patients NAD after course 1 or at day 1 of week 13 in patients NAD or AD better after course 2 until the end of month 12.

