### **9.2.1.3 Continuation treatment**

The overall therapy duration is 6 months for Arm LR 6 or 12 months for Arm LR 12 .

Pulses of oral prednisone PDN 40mg/m^2 in 3 doses, day 1-5 q 3 weeks, starting at day 1 of week 7 in patients NAD after course 1 or at day 1 of week 13 in patients NAD or AD better after course 2 until the end of month 6 or 12 from therapy start.

Vinblastine (VBL) 6mg/m^2 i.v. bolus, day 1 q 3 weeks, starting at day 1 of week 7 in patients NAD after course 1 or at day 1 of week 13 in patients NAD or AD better after course 2 until the end of month 6 or 12 from therapy start.

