## **16.6 STOPPING RULES**

In patients without “RISK” organ involvement experience from LCH-II indicate that only a limited number of toxicities can be expected. Therefore for this subgroup no stopping rules will be implemented. Stopping rules for organ toxicity and early deaths are implemented only for patients with “RISK” organ involvement. In LCH patients the differentiation between treatment related toxicity and disease related organ dysfunction (liver, hematopoiesis, mucous membranes and skin) may present a diagnostic dilemma. For this reason organ dysfunction will be assessed according the WHO toxicity score already at diagnosis and throughout the follow up. Clear toxic events should be reported immediately. Interim analyses on severe organ toxicity (WHO score grade III-IV) within the first 12 weeks of therapy will be performed twice a year. The rate of severe organ toxicity within the first 12 weeks of therapy of both treatment arms will be compared by Fisher’s exact test. A group sequential design according to Pocock will be applied to account for repeated significance testing to assure an overall significance level of  $\alpha = 5\%$ . In addition we will monitor early deaths within the first 6 weeks of therapy. In arm A of the LCH II study, 5 early deaths within 12 weeks of therapy were observed among 50 patients (10%, 95% CI 5% – 23%). Based on this previous experience, we consider an early death rate below or equal to 10% as acceptable. An early death rate of 15% as unacceptably high. We will perform Wald’s sequential ratio test. The upper boundaries

we will use will be shown in figure 7.

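### The planned 12-week toxicity comparison closes before the two Group 2 arms diverge, so it says nothing about the toxicity of 12 versus 6 months of therapy

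*Protocol*

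**What the plan says.** Toxicity is on the single list of secondary endpoints in section 16.2.2, which serves both randomised trials. Section 16.3 adds "A separate analyses will be performed for each group", RISK and LOW RISK. Section 6.2.3 sets a goal for Group 2: "To assess acute and late treatment toxicity". Section 6.1.3 sets the same goal for Group 1.

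The analysis is fixed in section 16.3.2: the proportion with "severe organ toxicity (WHO score grade III-IV) within the first 12 weeks of treatment will be compared" by Fisher's exact test. No group is named in that sentence.

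Section 16.6 holds a second comparison: "Interim analyses on severe organ toxicity (WHO score grade III-IV) within the first 12 weeks of therapy will be performed twice a year", with a Pocock design. It applies to patients with risk-organ involvement only. For patients without such involvement the section cites LCH-II experience that "only a limited number of toxicities can be expected. Therefore for this subgroup no stopping rules will be implemented".

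The Group 2 treatment contrast is in section 9.2.1.3: "The overall therapy duration is 6 months for Arm LR 6 or 12 months for Arm LR 12". Section 16.1.2 places Group 2 randomisation after the week-6 response evaluation. Section 16.3.1.2 starts the efficacy interval six months after therapy start, because that is when one arm is meant to stop and the other to go on.

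**The concern.** Group 2 asks whether six more months of prednisone and vinblastine prevent enough reactivations to be worth giving. An answer needs the benefit and the added toxicity over the same contrast. The efficacy analysis is aligned with the point where the arms part; the toxicity analysis is not. It ends at week 12, while both arms are still on the same planned treatment.

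Whatever the extra six months do, the expected difference in this window is zero. Any difference that is found is chance. An absence of difference would be uninformative, but could be mistaken for evidence on treatment duration. Section 16.4 also names toxicity among the considerations for stopping or continuing a trial once the inner boundary is crossed. For Group 2, no comparison by arm is planned that could inform that decision.

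**Working it through.** **Plan's own figures.** The toxicity comparison has no stated rate, power or sample size. The Group 2 design figures in section 16.5.2 reproduce approximately and are not affected by this point:

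- Hazard ratio: ln(0.85)/ln(0.65) = 0.377.
- Events, fixed design: 4 × (1.960 + 0.842)² / (ln 0.377)² = 33.0.
- With the inflation the protocol uses in Group 1 (228/202 = 1.129): 33.0 × 1.129 = 37.3, against 36 stated.
- Recruitment: 24 per year × 6 years = 144, against 148 stated.

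**Overlap of window and contrast, Group 2** (sections 9.2.1.3, 16.1.2, 16.3.1.2, 16.3.2)

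| Period from therapy start | LR 6 and LR 12 | In the 12-week window? |
|---|---|---|
| Weeks 1-6 | not yet randomised | yes |
| Weeks 7-12 | same planned continuation | yes |
| Week 13 to month 6 | same planned continuation | no |
| Months 6-12 | LR 6 stops, LR 12 continues | no |

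Six months is 52.18/2 = 26.1 weeks. The overlap is 0 of about 26 weeks. At one cycle every three weeks, the uncompared exposure is 26/3, or about 9 vinblastine doses and prednisone pulses per LR 12 patient.

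**What the planned test can return in Group 2.** The null hypothesis is true by design in this window. Taking 148/2 = 74 per arm and an assumed common toxicity rate (the protocol gives none), the exact probability that a two-sided 5% Fisher test rejects is:

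| Common rate | 2% | 5% | 10% | 20% | 30% |
|---|---|---|---|---|---|
| Rejection | 0.2% | 1.5% | 2.7% | 3.0% | 3.2% |

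These are type I errors. They do not depend on how toxic months 6-12 are.

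**Is there a substitute elsewhere?**

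- The section 16.6 comparison has the same window and excludes Group 2.
- The biannual DSMB review in section 15 covers toxicity reports, with no comparison by arm specified.
- Permanent consequences are defined in section 2 as results of the disease, so they do not measure drug toxicity.
- Section 16.6 relies on LCH-II experience for Group 2. Section 2 puts LCH-II treatment at only six months, so that experience does not reach months 6-12.

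**What a month 6-12 comparison could show.** Exact Fisher power at 74 per arm, all rates assumed:

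| LR 6 vs LR 12 | Power |
|---|---|
| 2% vs 5% | 5% |
| 2% vs 10% | 40% |
| 2% vs 15% | 78% |
| 2% vs 20% | 95% |
| 5% vs 15% | 44% |
| 5% vs 20% | 75% |
| 5% vs 25% | 92% |

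Only large excesses would be detected. At 5% vs 15% the approximate 95% half-width for the difference is 1.96 × √[(0.05 × 0.95 + 0.15 × 0.85)/74] = 9.5 percentage points. An estimate with its interval is more useful than a test.

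**Group 1, for comparison.** The window covers 12 of 52 weeks (23%), including all intravenous methotrexate. Arm B's continuation methotrexate is given "orally, once weekly until the end of month 12" (section 9.1.2.3). Patients starting continuation at week 13 have 0 of about 40 weekly doses in the window. Those NAD after course 1 start at week 7 and have 6 of about 46 (13%). The window misses about 87% to 100% of this phase.

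**The case against.** **The sentence may be meant for Group 1.** It repeats the endpoint, window and test of section 16.6, which is for RISK patients, and it fits the week-12 primary endpoint of Group 1. Section 16.3.2 also mixes group-specific items without labels. This is plausible, but the sentence names no group, and section 16.3 calls for separate analyses by group. On the Group 1 reading, Group 2 has no planned toxicity comparison at all despite goal 6.2.3. Either way the text needs correcting.

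**A statistical analysis plan could add later windows.** It could, and silence on such detail would be no finding. Here the protocol is not silent: it states a window, and for Group 2 that window is uninformative.

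**Secondary analyses are exploratory.** True. The primary endpoints, significance level, sample size and boundaries are untouched.

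**Readings that go too far.** A reader might infer that the trial cannot measure later toxicity. The documents do not support that: there is a toxicity sheet (section 9.5), immediate reporting of serious events (9.5.1), DSMB review (15) and WHO scoring throughout follow-up (16.6). What is missing is a comparison. A reader might also infer that Group 1 omits oral methotrexate altogether; for patients NAD at week 6, six weekly doses fall inside the window.

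**Group 1 selection.** One might want a Group 1 comparison from week 13 that ends at a switch to salvage. That objection stands. At the planned non-response rates and 228/2 = 114 per arm, about 114 × 0.50 = 57 patients in arm A and 114 × 0.70 = 80 in arm B would remain on assigned treatment. Such a comparison would set responder subsets selected after randomisation against each other and depart from the intention-to-treat rule in section 16.3.

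**Conclusion.** The point holds for Group 2. As written, the between-arm toxicity comparison overlaps 0 of about 26 weeks of differing planned exposure. It carries no information on the toxicity of 12 versus 6 months of therapy and does not serve goal 6.2.3. This follows from the protocol's own dates and needs no assumed rate. The rejection and power figures do rest on assumed toxicity rates and on 74 patients per arm.

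For Group 1 the 12-week window is defensible, since it covers all intravenous methotrexate and precedes most switching to salvage. It leaves out most of the oral methotrexate phase, which calls for at most a descriptive addition. Nothing here shows that longer therapy is more toxic, or that the trial will report it as no more toxic.

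**What to change.** In section 16.3.2:

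1. State that the 12-week comparison serves Group 1.
2. For Group 2, compare the proportion with WHO grade III-IV organ toxicity from month 6 to month 12 after therapy start, plus a fixed post-treatment period whose length is stated in advance. Analyse by allocated arm under intention to treat and count all patients whatever further treatment they receive. This matters because section 10.3.2 lets some LR 6 patients receive treatment after month 6, which dilutes the contrast. Report the difference with a confidence interval.
3. Give this Group 2 tally by arm to the DSMB at its existing biannual toxicity review (section 15).
4. For Group 1, at most add a descriptive summary by allocated arm to month 12, without censoring at a switch to salvage.

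The cost is wording and one table for Group 2, with a second table if the Group 1 summary is added. WHO scores are already to be collected throughout follow-up, and neither treatment nor sample size changes. The small downside is that toxicity sheets must be complete to month 12 in LR 6 as well, where patients are meant to be off treatment.
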